Cancer patients undergoing surgery treatment	
It has been well established that major surgery itself increases the risk of VTE even in the absence of cancer. [9]. Historical data from 1970s and 1980s using routine screening procedures reported a 37% incidence of deep vein thrombosis (DVT) following general surgery in patients with cancer, in contrast to an estimated risk of 20% in patients without cancer. [10]. However, changes in surgical techniques, use of perioperative chemotherapy, and the practice of early postoperative mobilization with increased awareness of perioperative VTE likely have altered VTE incidence over time.
 
The absolute VTE risk varies with the type of surgery, including site, technique (e.g., open vs. laparoscopic approach), duration of surgery, type of anesthesia, the presence of postoperative infection and immobilization, and patients' comorbidities (e.g., body mass index [BMI] and previous history of VTE). Surgeries for resection of malignant tumors are associated with a particularly high risk of VTE likely because of the extensive vascular injury from tumor invasion and dissection as well as lengthy operation time, and in some cases, residual tumor or nodal mass continues to cause venous compression and stasis. Prolonged postoperative immobility is also quite common in these patients.
 
The risk of thrombosis is not only increased during the immediate postoperative period but also extends at least up to 30 days or even longer after surgery. In the @RISTOS study that prospectively followed 2,373 patients who underwent surgery for cancer, 40% of symptomatic VTE occurred more than 3 weeks after surgery and 46% of deaths were due to fatal pulmonary embolism (PE). [11] The investigators of the @RISTOS study found that a previous history of VTE, anesthesia lasting 2 hours or longer, bed rest for 4 days or longer, advanced tumor stage, and age 60 years or older were significant risk factors for VTE. Similarly, in the Million Women Study, the incidence of symptomatic VTE was observed to peak at 3 weeks postoperatively for all surgeries, but the risk remained

high up to 4 to 12 months for cancer patients.[12]. Relative to patients without cancer, the risk of VTE after surgery for cancer was 91-fold higher at 6 weeks, 53-fold at 7 to 12 weeks, and 34-fold at 4 to 12 months after surgery.

Estimated risk of venous thromboembolism associated with various types of surgery 13

Surgical setting	Incidence of DVT, %	Incidence of PE, %
Major abdominal and pelvic surgery (colorectal/gynecological)	15–40 ^a	1.3–2 ^d
Major open urological surgery	15–40 ^a	0.2 ^e
Neurosurgery	15–40 ^a	Insufficient data
Thoracic surgery	4–14 ^a	5–12 ^f
Breast surgery	0.8–2.1 ^b	Insufficient data
Laparoscopic surgery	1–11 ^c	Insufficient data

Abbreviations: DVT, deep vein thrombosis; PE, pulmonary embolism.

Source: Adapted and modified from Geerts et al.¹⁶

^aRoutine screening of asymptomatic patients without prophylaxis.

^bSymptomatic patients without prophylaxis or mechanical prophylaxis alone (from retrospective studies).

^cRoutine screening of asymptomatic patients with or without prophylaxis.

^dSymptomatic patients without prophylaxis.

^eSymptomatic patients without prophylaxis or mechanical prophylaxis alone.

^fRoutine screening of asymptomatic patients with CT chest.

Pharmacological Prophylaxis

Pharmacological Prophylaxis for cancer patients undergoing surgery

Studies in the late 1980s and early 1990s showed that pharmacological prophylaxis reduces the risk of postoperative VTE by 60% compared with no prophylaxis.[14-17]

LMWH is generally the preferred choice of anticoagulant over UFH based on its ease of administration (once daily vs. twice to three times per day for UFH) and lower risk of heparin-induced thrombocytopenia (HIT).

Cancer patients may also tolerate higher doses of LMWH without increasing the bleeding risk further.[18]

The optimal duration of thromboprophylaxis after cancer surgery has not been established and the available data are limited to major abdominal and pelvic surgery. Although studies have shown that a longer duration of prophylaxis up to 1 month after major abdominal and pelvic surgery can further reduce the risk of VTE compared with standard duration (typically while in hospital or up to 7–10 days) [19-21]

In the ENOXACAN II trial, patients who received extended thromboprophylaxis (ETP) with LMWH up to 30 days after open surgery for abdominal and pelvic cancer had a 60% VTE risk reduction (95% CI: 10–82%), compared with those who received standard duration of 6 to 10 days (4.8 vs. 12%; $p = 0.02$).[19]

These findings are supported by a recent meta-analysis of seven RCTs and prospective studies which concluded that ETP is associated with a significant risk reduction of all VTE (2.6 vs. 5.6%; (RR: 0.44, 95% CI:

[figure not shown]
0.28–0.70) and proximal DVT (1.4 vs. 2.8%; RR: 0.46, 95% CI: 0.23–0.91). [22]

Consensus guidelines on primary thromboprophylaxis in cancer patients undergoing surgery

Guidelines for thromboprophylaxis for cancer patients undergoing surgery

Methods	Guideline	Recommendations
Pharmacological thromboprophylaxis	ACCP 2012	
 For general and abdominal-pelvic surgery and thoracic patients at high risk for VTE who are not at high risk for major bleeding complications, pharmacological prophylaxis with LMWH or LDUH is recommended over no prophylaxis. For craniotomy and spinal surgery patients at high risk for VTE, pharmacological prophylaxis should be added to mechanical prophylaxis once adequate hemostasis is established and risk of bleeding decreases
	ASCO 2015	
 All patients with malignant disease undergoing major surgical intervention should be considered for pharmacological thromboprophylaxis with either UFH or LMWH unless contraindicated Prophylaxis should be commenced preoperatively
	ESMO 2011	
 In cancer patients undergoing major cancer surgery (laparotomy, laparoscopy, thoracotomy, or thoracoscopy lasting more than 30 min), prophylaxis with LMWHs or UFH is recommended
Mechanical thromboprophylaxis	ACCP 2012	
 Mechanical prophylaxis with elastic stockings or IPC should be added to pharmacological prophylaxis in patient with high risk of VTE For high VTE risk general and abdominal-pelvic surgery patients, who are also at high risk for major bleeding complications, mechanical prophylaxis, preferably with IPC, is suggested over no prophylaxis until the risk of bleeding diminishes and pharmacologic prophylaxis may be initiated For high VTE risk patients in whom the consequence of bleeding might be severe, mechanical prophylaxis is suggested over no prophylaxis
	ASCO 2015	
 A combined regimen of pharmacological and mechanical prophylaxis may improve efficacy, especially in the highest risk patients Mechanical prophylaxis should not be used as monotherapy unless pharmacological methods are contraindicated
	ESMO 2011	
 Mechanical methods such as pneumatic calf compression may be added to pharmacological prophylaxis but should not be used as monotherapy unless pharmacological prophylaxis is contraindicated because of active bleeding
IVC filter	ACCP 2012	
 IVC filter should not be used for primary VTE prevention for all risk groups
	ASCO 2015	
 Not specified in primary prophylaxis setting
	ESMO 2011	
 Not specified in primary prophylaxis setting
Duration of thromboprophylaxis	ACCP 2012	
 Not specified
	ASCO 2015	
 7–10 d
	ESMO 2011	
 At least 10 d
Extended thromboprophylaxis	ACCP 2011	
 For high-risk patients undergoing abdominal or pelvic surgery for cancer who are not otherwise at high risk for major bleeding complications, extended duration pharmacologic prophylaxis (4 wk) with LMWH is recommended over limited-duration prophylaxis
	ASCO 2015	
 Extended prophylaxis with LMWH for up to 4 wk postoperatively should be considered for patients undergoing major abdominal or pelvic surgery for cancer who have high-risk features such as restricted mobility, obesity, history of VTE, or with additional risk factors
	ESMO 2011	
 Cancer patients undergoing elective major abdominal or pelvic surgery should receive in-hospital and postdischarge prophylaxis with LMWH for up to 1 mo after surgery

Abbreviations: IVC filter, inferior vena cava filter; LDUH, low-dose unfractionated heparin; LMWH, low-molecular-weight heparin; UFH, unfractionated heparin; VTE, venous thromboembolism.

Introduction for cancer patients undergoing chemotherapy

Venous Thromboembolism (VTE) is a frequent malignancy complication which often results in serious health deterioration and death. The risk of deep vein thrombosis (DVT) and pulmonary embolism (PE) is considerably higher in cancer patients, compared to general population four to seven times [23, 24]. Venous thromboembolism is the second leading cause of death in patients with cancer and overall mortality is increased among patients who have both conditions. [25, 26, 27]

Evidences suggest that Thromboembolism risk could be cancer related, patient related or treatment related. This risk is highest for patients with certain types of solid tumors (stomach, pancreas, lung, gynecologic, bladder, testicular) and hematologic cancers and is increased for patients who are receiving chemotherapy 6.5 times [28] or radiotherapy, who have undergone operative procedures, who have metastatic disease, or who have inherited thrombophilias. Studies have indicated that the mechanisms of this effect may include mucin production by tumors, exposure of tissue factor rich surfaces and tissue factor bearing microparticles, cysteine proteinase production leading to thrombin generation, and local hypoxia. [28,29,30]

The development of VTE in cancer patients is associated with several adverse consequences including worsened short- and long-term prognosis and survival, mortality, morbidity, chemotherapy postponement, potential hospitalization, need for long-term anticoagulation with attendant bleeding complications and high rates of recurrent VTE [31,32]. In addition, VTE leads to significant consumption of health care resources; [33]. Therefore the optimal prevention and treatment of VTE are crucial components of patient care in this population. Currently, Low!Molecular! Weight Heparin (LMWH), is the gold standard for the CAT management for the last 15 years [34-36]

Moreover, in a variety of high-risk thrombosis clinical settings, LMWHs agents are safe and effective in preventing VTE [37-38]. Multiple randomized trials of thromboprophylaxis have been conducted focusing on ambulatory cancer patients receiving chemotherapy [39-40] . ESMO and ASCO current guidelines suggest considering thromboprophylaxis in high-risk ambulatory cancer patients with LMWHs.

Several contemporary studies have investigated independent predictors for VTEs in patients actively receiving chemotherapy leading to the development of risk models for identifying patients at highest risk. [41] The Khorana model is a validated scoring system that utilizes specific patient characteristics and laboratory values to stratify patients into low, intermediate, or high risk for venous thromboembolism;

Moreover, chemotherapy and thrombosis for over three decades, it remains an underappreciated risk that has not been routinely incorporated into thrombosis risk assessment models.[42] Cytotoxic chemotherapy has a multifactorial contribution to the risk of thrombosis. It induces vascular injury through apoptosis. In the case of cisplatin, this leads to release of prothrombotic particles that trigger thrombin generation via tissue factor independent mechanisms along with drastically increased vWF activity. Other agents, like 5-FU, also drive thrombin formation in combination with depleted protein C activity. L-asparaginase administration is tied to drastically decreased protein C, protein S, and antithrombin levels, creating a prothrombotic milieu through loss of anticoagulant factors. VEGF inhibition does not directly lead to thrombosis, but instead 'primes' the endothelium through a VEGF starved state to be more susceptible to injury. Additionally, platelet activation through PAR-1 and increased Gp IIb/IIIa activity in the case of immunomodulatory agents or increased vWF among others in the case of small molecule inhibitors contributes to this 'primed' state.[43-81]

Cancer patients undergoing systemic treatment for their malignancy are among the highest risk populations for thromboembolic complications; often, the treatment itself contributes to this risk. Recognition of the antineoplastic agents most likely to cause thrombosis can help raise provider awareness and lead to earlier diagnosis and treatment.

In our approach, we will protect our patient taking under consideration their treatment (surgery either chemotherapy)

Study Objective

In this study we will collect Real World Data of our clinical practice regarding Thromboprophylaxis in high thrombotic risk solid tumors patients undergoing surgical and /or chemotherapeutical treatment, for one year following the protocol initiation date.

- **Specifically we will focus on the following :**
 - Number of thrombotic events
 - Anti-thrombotic management dosage & duration
 - Any bleedings related to anticoagulation
 - Patients' adherence and compliance

Study Design

This is a prospective, phase IV, observational, non-interventional cohort study that aims to record the daily clinical practice regarding thromboprophylaxis in high thrombotic risk cancer patients (under surgery or chemotherapy) initiated December 2018 for a year time. Patients demographic data, cancer type and stage, anticoagulant treatment dose & duration, efficacy (VTE events), safety (bleedings) and information about adherence will be collected; more than one outcomes could be recorded.

Subject Completion/Withdrawal

Subjects may withdraw from the study at any time without prejudice to their care. They may also be discontinued from the study at the discretion of the Investigator for lack of adherence to study treatment or visit schedules, AEs, or due to termination of study observation period. The Investigator may also withdraw subjects who violate the study plan, or to protect the subject for reasons of safety or for administrative reasons. It will be documented whether or not each subject completes the clinical study. If the Investigator becomes aware of any serious, related adverse events after the subject completes or withdraws from the study, they will be recorded in the source documents and on the CRF.

Clinical Adverse Events

Clinical adverse events (AEs) will be monitored throughout the study.

Adverse Event Reporting

Since the study procedures are not greater than minimal risk, SAEs are not expected. If any unanticipated problems related to the research involving risks to subjects or others happen during the course of this study (including SAEs) these will be reported in accordance with current regulations. AEs that are not serious but that are notable and could involve risks to subjects will be summarized in narrative format.

Authorized staff will perform periodic site visits to review CRFs for completeness, but will have no direct access to patient records; although they could request further information from the hospital staff. The anonymized data will be collated centrally and entered into an electronic database using double data entry where appropriate. Any discrepancies identified by electronic logic checks and will be resolved using data clarification forms sent to sites.

Ethics committee approval will be obtained where approval of a prospective non-interventional study is required. This study will be conducted in full accordance all applicable Research Policies and Procedures and all applicable laws and regulations. The investigators will perform the study in accordance with this protocol, will obtain consent, and will report unanticipated problems involving risks to subjects or others in accordance with Policies and Procedures and all regulatory

requirements. Collection, recording, and reporting of data will be accurate and will ensure the privacy, health, and welfare of research subjects during and after the study.

Subject Population **Inclusion Criteria**

key criteria for Inclusion and Exclusion:

1. Patients who were diagnosed with histological confirmed high thrombotic risk cancers (GI, thoracic, gynecologic and genitourinary) undergoing surgery
2. Age \geq 18 years

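### Investigators may take patients out of the study for non-adherence, missed visits or AEs, and the documents describe little outcome recording after that exit, so later VTE, bleeding and adherence data may be lost selectively

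*Combined protocol and SAP*

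**What the plan says.** The Study Objective lists four items of interest. Three matter here: "Number of thrombotic events", "Any bleedings related to anticoagulation" and patients' "adherence and compliance". Study Design calls the study a prospective, non-interventional cohort that "aims to record the daily clinical practice regarding thromboprophylaxis".

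Subject Completion/Withdrawal allows subjects to be "discontinued from the study at the discretion of the Investigator for lack of adherence to study treatment or visit schedules, AEs". It adds withdrawal for violating the study plan, for administrative reasons, or "to protect the subject for reasons of safety". Completion status is kept: "It will be documented whether or not each subject completes the clinical study". For the time after exit, the section provides for recording "serious, related adverse events after the subject completes or withdraws from the study", on condition that the investigator becomes aware of them.

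Study Duration runs each patient from enrolment to a follow-up visit four weeks after hospital discharge, where that visit applies. Study Phases describes the observation period as monitoring during treatment, again with follow-up only where applicable. The Statistical And Analytic Plan is descriptive and covers all study data. It lists the number enrolled and the number of therapy disruptions, but gives no rule for patients who were discontinued. The Appendix lists a case report form that is not reproduced.

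**The concern.** In a cohort meant to describe routine practice, a patient who stops injections, misses a visit or bleeds is part of what is being described. The withdrawal rule lets the investigator end that patient's participation for these very reasons. Whether later data exist can then depend on the outcomes being measured, and analysing every record that was collected does not recover events that were not collected.

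What is at stake is the study's main product: the VTE count, the bleeding count and the adherence figure. The rule is also discretionary without guidance, so investigators may apply it differently. The background section on cancer surgery says that thrombotic risk persists for at least 30 days after the operation, so a VTE after an early exit but before the planned end of participation is plausible.

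**Working it through.** The plan states no sample size, event target or discontinuation rate, so there is no figure to reproduce. The check is a comparison of sections.

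**Step 1: do the exit grounds overlap with the outcomes?**
- Lack of adherence to treatment is an exit ground. Adherence and compliance are an objective.
- AEs are an exit ground. A bleed or a VTE can be an AE, and both event types are objectives.
- Missed visits are an exit ground and one form of non-compliance.

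They overlap. Study Design also expects that a patient may have more than one outcome; removal after a first AE could keep a second from being seen.

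**Step 2: what is described after exit?** The late-event sentence has three conditions: the event is serious, it is related, and the investigator learns of it. Set against the objectives:

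| Outcome | Fits the late-event sentence | May be missed |
|---|---|---|
| VTE | Serious, judged related, and known | VTE judged unrelated (for example, attributed to the cancer); VTE not reported back |
| Bleeding | Serious, judged related, and known | Non-serious bleeds, although Safety Evaluations collects clinically relevant non-major and minor bleeding; bleeds not reported back |
| Adherence | Not an adverse event | All adherence after exit |

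The VTE gap is the clearer one. For bleeding, the relatedness condition largely matches the objective if it means related to anticoagulation, which the withdrawal section does not say.

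**Step 3: does another section restore the data?** AE monitoring runs throughout the study, with no stated extension beyond removal. Study Phases ties observation to treatment time. The Statistical And Analytic Plan does not say how discontinued patients are counted. None of these describes continued VTE or bleeding recording after exit.

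**Step 4: can it be sized?** Let
- w = share of enrolled patients discontinued by the investigator,
- k = their VTE risk relative to patients who stay,
- m = share of their VTE within the planned observation window that falls after exit and is not captured.

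With all enrolled patients as the denominator:

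share of VTE missed = w·k·m / (1 − w + w·k)

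This is zero if w = 0 or m = 0. The documents give none of the three quantities. The background does report, from one prospective cohort of 2,373 cancer-surgery patients, that 40% of symptomatic VTE came more than 3 weeks after surgery. That figure cannot stand in for m. It fixes an exit time that the plan does not, and it does not say how many of those late events fall before four weeks after discharge. Events beyond that point lie outside planned follow-up for every patient and are not lost through removal.

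**The case against.** The strongest reply has four parts.

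*The late-event sentence is a safety minimum.* It applies to completers as well as to withdrawn patients and does not forbid other recording. This stands. A reader might infer that the plan stops all outcome recording at exit; the text does not say so. What can be said is that no other recording after exit is described, and that the case report form, which might provide for it, cannot be seen.

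*All enrolled patients may well be analysed.* The analysis plan covers all study data and lists the number enrolled. This also stands. A reader might infer that results will be reported for completers only and that adherence will therefore be inflated. No section adopts that basis. Adherence would be overstated only if discontinued patients left the denominator or their later non-adherence went unrecorded. A full denominator does not, however, supply events that were never recorded.

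*The rule is discretionary and the study descriptive.* The triggering event should already be on record, completion status is documented, and correlations serve only to assess hypotheses. These points limit the consequence. They do not remove the gap, because counts and proportions are what a descriptive study delivers.

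*Part of the loss comes from how observation is defined.* If observation ends with treatment, a patient who stops prophylaxis for good may already have reached its end, and the withdrawal rule then adds little. This is fair. It is a separate inconsistency, but it has to be settled before anyone can say until when data should be collected.

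**Conclusion.** The point holds as a risk created by a stated rule. Investigators may end study participation on grounds that overlap with the study's own outcomes, and the documents describe little outcome recording afterwards. If the discretion is used, data may be lost selectively, most clearly for VTE judged unrelated, then for non-serious bleeds and later adherence. Missed events can only lower the event counts.

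The documents do not support a claim that bias has occurred or will occur, and the size cannot be determined from them. The conclusion rests on two assumptions: that some patients are discontinued on these grounds before their planned end of participation, and that the case report form does not already provide for outcome recording after exit. Confidence is high on the gap in the text and limited on its consequence. This is a cheap improvement worth making.

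**What to change.** 1. In Subject Completion/Withdrawal, state that non-adherence, missed visits and AEs are recorded as outcomes and do not by themselves end data collection.
2. For patients discontinued by the investigator, continue to record VTE regardless of relatedness, and bleeding with relatedness noted. Use routine records or usual-care contacts, in keeping with the non-interventional design. Continue to the same planned end of participation as for other patients, unless consent is withdrawn, the patient dies or is lost to follow-up.
3. Reconcile Study Duration with Study Phases, so that this end of participation is defined.
4. In the Statistical And Analytic Plan, state that all enrolled patients are analysed, and report discontinuations with date and reason. Add both fields to the case report form if they are not already there.

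Clinical decisions on treatment and on withdrawal for safety stay as they are; the change concerns only what is recorded. The cost is a rewording of a few sentences, some extra record checks for discontinued patients, and possibly a less favourable adherence or VTE figure.

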Major bleeding will be defined as overt bleeding associated with: a fall in hemoglobin of 2 g/dL or more, or leading to a transfusion, or bleeding that occurs in a critical site or contributing to death.

- **Bleeding in a critical area or organ such as:**

Retroperitoneal

Intracranial

Intraocular

Intraspinal

Intra-articular

Pericardial

Intramuscular with compartment syndrome

- **A clinically overt bleeding event**
 - that is associated with a fall in hemoglobin of 2.0 g/dL (>1.24 mMol/L) or more, or
 - leading to a transfusion of ≥ 2 units of packed red blood cells or whole blood.
- **Bleeding contributing to death**

Other clinically relevant non-major bleeding will be defined as overt bleeding not meeting the criteria for major bleeding but associated with medical intervention, unscheduled contact (visit or telephone call) with a physician, (temporary) cessation of study treatment, or associated with discomfort for the patient such as pain, or impairment of activities of daily life. All other bleeding events will be classified as minor

Statistical And Analytic Plan	
Descriptional statistical analysis will be performed for all study data along with epidemiology methods. Continuing parameters will be presented with standards descriptional statistical measures (mean values, median values, percentages etc.) and the results will be presented accordingly into tables. For more complex correlations we will use, among other methods, chi-square tests, ANOVA and t-tests, in order to evaluate the relationships between different patient and disease characteristics, such as:
 
 • Number of patients enrolled • Tumor characteristics • Co-morbidities • Type of Surgical operation • Type of antineoplastic treatment • Type of thromboprophylaxis therapy • Therapy outcomes • Number of therapy disruptions for any reason • Complications (AE- SAE) 
and to present them, accordingly. Due to the fact that this is an observational study the results of all correlations will be carefully discussed and will be used only to assess hypotheses.

REFERENCES	References

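### Several sites are implied but no analysis is stated to account for site, so outcome comparisons by prophylaxis type may be confounded by hospital and their p-values may be too small

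*Combined protocol and SAP*

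**What the plan says.** The last paragraph under Adverse Event Reporting describes data handling. It says "Authorized staff will perform periodic site visits to review CRFs for completeness", that "The anonymized data will be collated centrally and entered into an electronic database", and that discrepancies "will be resolved using data clarification forms sent to sites". Together these imply several sites. The text available for review gives no number of sites. Front matter was not available, so I do not count the missing number as a fault.

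The Study Objective speaks only of "In this study we will collect Real World Data of our clinical practice regarding Thromboprophylaxis". Study Design calls the study observational and non-interventional, so prophylaxis is whatever routine care delivers.

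The Statistical And Analytic Plan is one paragraph with a list. After descriptive statistics it says "we will use, among other methods, chi-square tests, ANOVA and t-tests", to be used "in order to evaluate the relationships between different patient and disease characteristics". The list that follows includes "Type of thromboprophylaxis therapy" and therapy outcomes. Site or hospital is not on the list, and is not mentioned anywhere as a covariate, stratum, cluster or random effect. No adjusted model is named. The paragraph closes by limiting correlations to the assessment of hypotheses.

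**The concern.** Two separate problems can arise when site is left out of a comparison of outcomes by prophylaxis type.

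The first is confounding. If hospitals differ in which prophylaxis they use and also in their underlying event rate, the crude comparison mixes the two. Event rates could plausibly differ. The protocol's own background table gives DVT incidence of 15–40% for major abdominal and pelvic surgery and 4–14% for thoracic surgery, so hospitals with different surgical case mix could have different rates whatever prophylaxis they use. Incidental PE and DVT also count as events, so local imaging habits could affect how many are found.

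The second is clustering. The three named tests, in their standard form, treat patients as independent. If both prophylaxis use and outcome cluster by site, the true standard error is larger than the one the test uses, and the p-value is too small.

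At stake is whether a difference between hospitals is reported as a difference between prophylaxis types.

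**Working it through.** The plan states no sample size, significance level, number of sites, patients per site or intraclass correlation (ICC), so there is no figure of its own to reproduce. Every site-level input below is an assumption.

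**1. Clustering, type wholly fixed by site.** With m patients per site (equal sizes) and outcome ICC ρ, the variance inflation is DE = 1 + (m − 1)ρ. The true two-sided error of a nominal 5% test is 2 × [1 − Φ(1.96/√DE)].
- m = 10, ρ = 0.01: DE = 1 + 9 × 0.01 = 1.09; error 0.060.
- m = 50, ρ = 0.10: DE = 1 + 49 × 0.10 = 5.9; error 0.420.

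**2. Clustering, type partly fixed by site.** With exposure ICC ρx, DE = 1 + (m − 1) × ρx × ρ. Taking ρx = 0.3 and the same two corners:
- DE = 1 + 9 × 0.3 × 0.01 = 1.027; error 0.053.
- DE = 1 + 49 × 0.3 × 0.10 = 2.47; error 0.212.

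**3. Type balanced within every site.** The true standard error is √(1 − ρ) times the naive one. For ρ = 0.01 to 0.05 the ratio is 0.995 to 0.975 and the error 4.9% to 4.4%. The naive test is then slightly conservative.

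**4. Check by simulation.** Pearson chi-square test with beta-binomial site risks, 10 sites of 50 patients, 5% event rate, no true effect, 20,000 runs per cell; true error of a nominal 5% test:

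| Use of a given type | ICC 0.01 | ICC 0.02 | ICC 0.05 |
|---|---|---|---|
| Fixed by site | 10.9% | 16.1% | 28.5% |
| 80% in half the sites, 20% in the rest | 7.0% | 8.8% | 14.0% |
| Balanced within site | 4.5% | 4.6% | 4.4% |

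The formula at m = 50 with type fixed by site gives 10.8%, 16.4% and 29.1%, so the two agree closely.

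**5. Confounding.** Take two hospitals of equal size and no true effect of type. Hospital 1 has risk r1 and uses type A in a share s of its patients; hospital 2 has risk r2 and uses type A in 1 − s. The crude risk is s·r1 + (1 − s)·r2 on type A and (1 − s)·r1 + s·r2 on type B. As illustrative hospital risks I borrow two pairs of VTE rates from the protocol's background on extended prophylaxis; there they are trial-arm or pooled rates, not hospital rates.
- r1 = 2.6%, r2 = 5.6%, s = 0.8: A = 0.8 × 2.6 + 0.2 × 5.6 = 3.2%; B = 0.2 × 2.6 + 0.8 × 5.6 = 5.0%; crude risk ratio 3.2/5.0 = 0.64.
- r1 = 4.8%, r2 = 12%, s = 0.8: A = 6.24%; B = 10.56%; crude risk ratio 0.59.
- At s = 0.6 the two ratios are 0.86 and 0.84; at s = 0.5 both are 1.00.

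The size of the problem therefore depends on how unevenly types are used across sites. The documents do not say how prophylaxis is chosen.

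**The case against.** The best defence is that the plan is open rather than wrong. It promises epidemiological methods, names its tests as some among others, and introduces its variable list as examples. Nothing excludes site. The objectives are mainly descriptive, and the plan already says that correlations will be discussed with care and used only to assess hypotheses. No passage says that local policy sets prophylaxis, and if use is balanced within sites the naive test is, if anything, slightly conservative.

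Much of this stands, and it rules out several stronger readings that a reader might infer:
- That every planned test ignores site. The text supports only that no site-adjusted method is stated.
- That the comparisons are confounded, or their standard errors too small, as a matter of fact. Both are conditional on use and outcome varying by site.
- That comparisons of dose and duration are affected. These are items to be recorded under the Study Objective and Study Design; the analysis list names only type.
- That planned confidence intervals are too narrow. The plan mentions none, so the effect would fall on p-values and on any intervals reported later.

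What does not stand is the idea that the closing caveat settles the matter. Careful discussion cannot separate hospital from prophylaxis unless the data are shown or analysed by site. Type and outcomes are both on the list of things to be related, so the exposed comparison is a planned one.

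**Conclusion.** The concern holds in conditional form. Several sites are implied, no stated analysis accounts for site, and exposure follows routine practice. Outcome comparisons by prophylaxis type may therefore be confounded by hospital, and p-values may be too small if use and outcome both cluster by site.

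The size cannot be fixed from the documents. With 10 to 50 patients per site and an ICC of 0.01 to 0.10, the true error of a nominal 5% test is 6% to 42% if type is wholly site-determined. It is 5.3% to 21% at an exposure ICC of 0.3, and at or just below 5% if use is balanced within sites. The 42% is the extreme corner of assumed inputs and should not be read as an estimate for this study.

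Because the study is mainly descriptive and limits its own inference, this is a worthwhile improvement and not a serious defect.

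**What to change.** In the Statistical And Analytic Plan:
- State the number of sites, and tabulate prophylaxis type and the VTE and bleeding outcomes by site. The table shows directly whether type and site can be separated.
- For any comparison of outcomes by prophylaxis type, report a result stratified by or adjusted for site beside the crude one: Cochran-Mantel-Haenszel, or a site term or random site effect in a regression model. Stratification and a fixed site term compare patients within sites. A random site effect allows for clustering but does not by itself fully remove confounding by hospital.
- Where each site uses one type there is no within-site contrast, and Cochran-Mantel-Haenszel or a fixed site term cannot estimate the difference. Report such a comparison as descriptive only.

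The cost is a few sentences and one table. Site should be traceable for each record, since queries go back to sites, but this needs confirming because the case report form was not available. The statistical price is wider intervals, and sparse strata or unstable models if there are few events or few patients per site.
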